#### **Co-primary endpoint**

- Change in lumbar spine BMD from baseline to 6 months after the zoledronic acid infusion.
- The proportion of patients who fails to maintain BMD (total hip, femoral neck and spine). Failure is defined as  $\geq 3$  % BMD loss at the lumbar spine or  $\geq 5$  % BMD loss at the femoral neck or total hip.

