### Investigations

*Bone turnover markers:* Biochemical markers of bone turnover are s-bone alkaline phosphatase (s-BSAP), p-osteocalcin, p-PINP and p-CTX. The samples will be collected in peripheral blood samples in the morning (7:30–10:45 a.m.) after a minimum of eight hours of fasting, then centrifuged at 400 rpm at five degrees Celsius for ten minutes and stored at -80 degrees Celsius. P-CTX, p-osteocalcin and p-PINP will be analyzed on EDTA plasma using ELISA (Cobas 6000 immunoassay analyser, Roche Diagnostics GmbH) and BASP on serum using immunochemical reaction (ISYS). The samples will be analysed in a batch at the Department of Biochemistry, Aarhus University Hospital to reduce the analytical variation. The precision is  $\pm 7.4\%$  at 32  $\mu\text{g/l}$  (95% CI),  $\pm 10\%$  at 0.30  $\mu\text{g/l}$ ,  $\pm 6\%$  at 18  $\mu\text{g/l}$  and  $\pm 20\%$  at 44.4  $\mu\text{g/l}$  for p-PINP, p-CTX, p-osteocalcin and s-BSAP, respectively. If the results of any of the blood samples are below or above the detection range, we will use the lowest or highest detectable value, respectively. The BTMs will be measured at every clinical visit. If the specified p-CTX level is reached before month three (nine-months group) or month six (observation group) zoledronic acid will be administered.

*Biochemistry:* Markers of diseases affecting bone metabolism (calcium, phosphate, magnesium, 25-OH-vitamin D, PTH, creatinine, alkaline phosphatase, TSH). The samples will be analyzed at the Department of Biochemistry, Aarhus University Hospital.

*Bone mass:* Areal bone mineral density (aBMD) ( $\text{g/cm}^2$ ) of the lumbar spine (L1-L4) and hip (left) will be measured using a Hologic Discovery scanner (Hologic, Inc., Waltham, MA, USA). The right hip was scanned in case of prosthesis at the left hip. All participants were examined on the same DXA scanner throughout the trial. Incident vertebral fractures will be investigated using the vertebral fracture assessment (VFA) tool on the Hologic Discovery scanner. Lumbar spine trabecular bone score (TBS) will be measured using the TBS iNsight software, version 2.1.0.0 (Medimaps, Merignac, France).

*Bone quality:* Bone microarchitecture and estimated bone strength will be assessed by a high-resolution peripheral quantitative computed tomography (HR-pQCT) scan of the distal radius and tibia.

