### **Statistical analysis and power calculation**

Baseline characteristics of the three groups will be presented using descriptive analysis and compared using ANOVA and post-hoc unpaired t-tests if ANOVA demonstrates differences between the groups. Changes in bone mineral density one year after the zoledronic acid infusion within groups will be investigated using paired-sample t-tests and compared with the changes reported after stopping denosumab after two years [12] for the three groups combined and individually using one-sample t-test. The proportion of patients who fails to maintain BMD will be compared between groups using chi-sq test. Changes in bone mineral density, HRpQCT measures and markers of bone turnover will be compared between groups using mixed model analysis. Exploratory analyses will include multiple regression analyses aiming at identifying baseline factors or changes occurring at three or six months, which affect the change in BMD one year after the zoledronic acid infusion. Factors included in this analysis will be gender, age, years of treatment with denosumab, baseline BMD, baseline bone turnover markers, change in bone turnover markers three and six months after the zoledronic acid infusion.

Based on a previous study a 5% decrease in lumbar spine BMD can be expected during the first year after discontinuation with a 3% standard deviation [12]. The hypothesis is that treatment with zoledronic acid can decrease this bone loss. Eighteen patients will be needed to demonstrate a bone loss  $\geq 2.5$  % using a paired-sample t-test with a power of 90% and level of significance of 5%. If the decrease is less than that BMD is maintained and the hypothesis can be accepted. To account for dropouts n is increased to 20 in each group. As comparisons between the different treatment regiments suggested in this protocol never have been done before, we cannot estimate differences between groups. However, the least significant change in lumbar spine BMD using DXA is 3%. The SD of lumbar spine BMD in our facility is 3% [18]. To be able to demonstrate a difference in change in lumbar spine BMD between the three groups equal to the least significant change using independent samples t-test we need 16 patients in each group with a standard

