deviation of 3%, power of 80% and significance level of 5%. Thus, the already planned 20 participants per group are sufficient to make meaningful exploratory analyses. New participants will be enrolled after four dropouts in total. Per-protocol analysis will be performed.

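### The between-group mixed models state no baseline covariate; prespecifying each outcome's own baseline value would add precision at almost no cost if it explains more than about 2% of the variance

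*Combined protocol and SAP*

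**What the plan says.** The section on statistical analysis and power calculation gives the between-group model as "Changes in bone mineral density, HRpQCT measures and markers of bone turnover will be compared between groups using mixed model analysis". It lists no fixed effects, covariates or covariance structure. It does not say whether baseline is a covariate, a repeated outcome, or enters only through subtraction in the change.

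One co-primary endpoint is analysed this way: "Change in lumbar spine BMD from baseline to 6 months after the zoledronic acid infusion".

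Baseline variables appear as model terms only in a separate analysis: "Exploratory analyses will include multiple regression analyses aiming at identifying baseline factors or changes occurring at three or six months". Its candidate list begins "Factors included in this analysis will be gender, age, years of treatment with denosumab, baseline BMD, baseline bone turnover markers" and goes on to marker changes after the infusion. The Investigations section defines the marker group: "Biochemical markers of bone turnover are s-bone alkaline phosphatase (s-BSAP), p-osteocalcin, p-PINP and p-CTX".

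The between-group sample size uses an independent-samples t-test without covariates. The target difference comes from the statement that "the least significant change in lumbar spine BMD using DXA is 3" per cent. The other inputs are a "deviation of 3%, power of 80% and significance level of 5" per cent, giving 16 per group against 20 planned. The plan calls the between-group analyses that this number supports exploratory.

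The Randomization section describes blocks of 6 and no stratification factor. The study plan tables place DXA, HR-pQCT and bone markers at the baseline visit for every group.

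**The concern.** Whether the timing of zoledronic acid matters is one of the trial's stated aims, and each arm has only 20 patients. If the baseline value of an outcome is related to its later change, a model without it leaves that variation in the residual, and the confidence intervals are wider than they need be. The data to avoid this are already collected.

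There is also a question of prespecification. The plan tests baseline characteristics by ANOVA, with post-hoc t-tests if groups differ, but does not say what follows from a difference. In an open-label trial with an unspecified model, the covariates could be chosen after baseline differences, or even outcomes, have been seen.

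**Working it through.** **Inputs from the plan.** Difference 3%, SD 3%, power 80%, significance level 5%, 20 per group, three groups. Sidedness is not stated; two-sided is assumed because it reproduces the plan's figure.

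**Input not in the plan.** R², the share of variance in BMD change explained by baseline covariates. It is assumed over a range from 0 to 0.3.

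**Step 1: the plan's own figure.** n per group = 2 × (1.960 + 0.842)² × (3/3)² = 15.7, rounded up to 16. This matches the stated 16. With the exact t distribution, 16 per group gives 78.1% power and 17 gives 80.7%, so the difference is a matter of rounding and approximation.

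**Step 2: unadjusted comparison at 20 per group.**
- SE = 3 × √(2/20) = 0.949.
- Error df = 60 − 3 = 57, critical t = 2.002, half-width = 2.002 × 0.949 = 1.90.
- Power for 3% from the noncentral t, noncentrality 3/0.949 = 3.16: 87.5%. A two-group t-test with 38 df gives 86.9%.

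**Step 3: adjusted comparison with q covariates.**
- Residual SD = 3 × √(1 − R²).
- Error df = 60 − 3 − q.
- Variance is multiplied by 1 + q/(df − 1) for expected chance imbalance in the covariates.
- For q = 1: df = 56 and the factor is 1 + 1/55 = 1.018. At R² = 0.2, SE = 3 × √0.8 × √(0.1 × 1.018) = 0.856 and half-width = 2.003 × 0.856 = 1.72.

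| Assumed R² | Half-width, baseline value alone | Power | Half-width, three covariates | Power |
|---|---|---|---|---|
| 0 | 1.92 | 86.9% | 1.96 | 85.6% |
| 0.1 | 1.82 | 90.1% | 1.85 | 89.0% |
| 0.2 | 1.72 | 93.1% | 1.75 | 92.2% |
| 0.3 | 1.60 | 95.7% | 1.64 | 95.1% |

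The three covariates are baseline BMD, baseline p-CTX and years of denosumab. At any given R² the larger set does slightly worse, so the extra terms pay only if they raise R².

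**Step 4: break-even.** Setting the adjusted half-width equal to the unadjusted one gives, for baseline alone, R² = 1 − (2.0025/2.0032)² / 1.018, or about 0.019. For three covariates it is about 0.056.

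**Step 5: after dropout.** With 18 analysable per group, unadjusted power is 83.7%. With baseline alone at R² = 0.2 it is 90.3%.

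These calculations treat one follow-up visit at a time. They do not model correlation between repeated visits, for which the documents give no figure.

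**The case against.** The strongest answer is that the plan is silent and has not declined to adjust. A mixed model may hold baseline as a covariate or as a repeated outcome, and either could recover the precision discussed here. That stands: the plan does not specify adjustment, and it should not be reported as having rejected it.

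Four stronger inferences are tempting, and the documents do not support them.
- *The plan names baseline BMD, p-CTX and denosumab duration as likely predictors.* It lists candidates in an exploratory search, together with gender and age, and refers to bone turnover markers as a group of four without singling out p-CTX.
- *Precision is certainly lost.* No R² is given. Below the break-even values, adjustment costs a little precision.
- *Chance imbalance biases the comparison.* Under randomisation such imbalance is random error that the standard error already reflects; the unadjusted contrast remains valid.
- *The comparison is underpowered.* At 20 per group it has about 87% power against the 80% sought, and 83.7% at 18. The main sample size also rests on a within-group paired test that this model does not affect.

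These points limit the weight of the finding but do not remove it. An unstated model still has to be written down, and including the outcome's own baseline is the better choice unless baseline explains almost nothing.

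**Conclusion.** The point holds as a recommendation on precision and prespecification. No baseline covariate is stated for the between-group models, although the values are available for every patient. Relative to the unadjusted half-width of 1.90, adjusting for the baseline value alone narrows the interval by about 4%, 9% or 16% at R² of 0.1, 0.2 or 0.3 (1.82/1.90, 1.72/1.90, 1.60/1.90). At R² = 0 it widens it by about 1% (1.92/1.90). The R² values are assumptions; the rest relies on the plan's SD of 3% for BMD change, 20 analysable patients per group and two-sided testing. The possible loss is negligible and the possible gain moderate. The planned comparison would still be valid without the change and would meet its own power target.

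**What to change.** Write the model out in the statistical section. For each outcome, analyse change from baseline with group, visit, group × visit and the study-entry value of the same measure as fixed effects. Model within-patient correlation by a patient random effect or an unstructured covariance. HR-pQCT has a single follow-up scan, so its model reduces to group and baseline value. Use the value from the baseline visit in all three groups, not a later scan taken near the infusion. Report the model without the baseline covariate as a sensitivity analysis.

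Baseline p-CTX and years of denosumab may be added to the BMD models if they are named before data are seen. Marker changes after the infusion, which are in the exploratory list, must not be adjustment covariates because they follow treatment.

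The cost is SAP wording and one degree of freedom per model, or three if the optional terms are added. No new measurement is needed.

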**Duration of study**

Included patients will be part of the study for up to 30 months. The primary endpoints will be investigated 12 months after infusion of zoledronic acid. The participants will receive a letter from the investigator after the termination of the study with information about the study results.

Study plan

Group 1: 6-month group	Baseline	M1	M3	M6	M12	M16	M20	M24
Informed consent	X							
Medical history	X							
Physical examination	X							
Bone markers	X	X	X	X	X	X	X	X
Biochemistry	X				X			
HR-pQCT	X				X			
DXA	X			X	X			X
Zoledronic acid treatment	X							
Fracture history	X				X			X
Telephone call						X	X	

Group 2: 9-month group	Baseline	M1+2 	M3	M4	M6	M9	M15	M19	M23	M27
Informed consent	X									
Medical history	X									
Physical examination	X									
Bone markers	X	X	X	X	X	X	X	X	X	X
Biochemistry	X						X			
HR-pQCT	X						X			
DXA	X		X			X	X			X
Zoledronic acid treatment			X							
Fracture history	X						X			X
Telephone call								X	X	

Group 3: Observation group	Baseline	M1-5 	M3	Mx 	Mx+1	Mx+2	Mx+6	Mx+12	Mx+16	Mx+20	Mx+24
Informed consent	X										
Medical history	X										
Physical examination	X										
Bone markers	X	X		X	X	X	X	X	X	X	X
Biochemistry	X							X			
HR-pQCT	X							X			
DXA	X		X	X			X	X			X
Zoledronic acid treatment				X							

Fracture history	X							X			X
Telephone call									X	X	

 M1 + M2: Month 1 and month 2 after baseline.

 M1 - M5: Month 1 to month 5 after baseline.

 Mx: months after baseline, depends on when the specified levels of p-CTX or BMD loss are achieved

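### The three-month marker change listed for the exploratory regression is not scheduled in the observation group, so any model using it covers at most 40 of 60 patients and two of the three arms

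*Combined protocol and SAP*

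**What the plan says.** The section Statistical analysis and power calculation describes exploratory multiple regression analyses that look for "baseline factors or changes occurring at three or six months, which affect the change in BMD one year after the zoledronic acid infusion". The next sentence gives the list: "Factors included in this analysis will be gender, age, years of treatment with denosumab, baseline BMD, baseline bone turnover markers", followed by the "change in bone turnover markers three and six months after the zoledronic acid infusion". Randomised group is not on the list. No method for missing covariates is given; the section says only that the analysis is per protocol.

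The visit tables are under Duration of study. The first runs "Group 1: 6-month group Baseline M1 M3 M6 M12 M16 M20 M24", with infusion at baseline. The 9-month group is infused at M3 and then sampled at M4, M6, M9 and M15 onwards. In the table headed "Group 3: Observation group" the columns after the infusion visit Mx are "Mx+1 Mx+2 Mx+6 Mx+12 Mx+16 Mx+20 Mx+24". Bone markers are ticked at every one of these visits in all three tables. Mx is defined as "months after baseline, depends on when the specified levels of p-CTX or BMD loss are achieved". The monitoring samples before infusion in that group are defined as "Month 1 to month 5 after baseline", so they count from baseline and not from infusion. The Investigations section ties marker measurement to clinical visits.

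**The concern.** The analysis text and the schedule use different time points for one arm. A covariate that is never scheduled for a whole randomised group is not ordinary sporadic missingness. A fit on complete cases drops that group, and imputation would have to borrow the value entirely from the other two arms.

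The trial asks whether the timing of infusion matters, and the observation group is the arm in which timing follows the patient's own turnover. Predictors found in a three-month model would describe only the two groups with a scheduled infusion. The plan does not say so, and a reader of the report could take them as applying to all three strategies.

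**Working it through.** **Reference figures.** The plan gives no sample size for the regression, so there is no figure of its own to reproduce on this point. Its two stated sizes belong to t-tests and both reproduce: 18 for the paired test (noncentral t, two-sided 5%: power 0.915 at 18 and 0.897 at 17) and 16 per group for the two-sample test (normal approximation). Neither bears on what follows.

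**Step 1: put the marker visits on the infusion clock.** Months since infusion = visit month − infusion month, from the tables under Duration of study.

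| Group | Infusion | Marker visits after infusion | Months since infusion |
|---|---|---|---|
| 6-month | Baseline | M1, M3, M6, M12, M16, M20, M24 | 1, **3**, 6, 12, 16, 20, 24 |
| 9-month | M3 | M4, M6, M9, M15, M19, M23, M27 | 1, **3**, 6, 12, 16, 20, 24 |
| Observation | Mx | Mx+1, Mx+2, Mx+6, Mx+12, Mx+16, Mx+20, Mx+24 | 1, **2**, 6, 12, 16, 20, 24 |

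The schedules agree everywhere except at the second sample. The observation table has 11 columns and its bone-marker row has 11 cells, so the absent Mx+3 is not a fault of text extraction.

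**Step 2: could the monitoring samples fill the gap?** They run from month 1 to month 5 after baseline. If they continued after an early infusion, a patient infused at month 1 would have a sample at M4 (1 + 3) and one infused at month 2 at M5 (2 + 3). The table does not say that they continue. For infusions at months 3 to 6 the three-month point falls at months 6 to 9, beyond the last monitoring sample.

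**Step 3: usable patients.** Planned sizes are 20 per group.
- With the three-month change: 20 + 20 + 0 = 40 of 60, a loss of 20/60 = 33%.
- With baseline factors or the six-month change only: 20 + 20 + 20 = 60.

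Both are maxima before dropouts. In the 9-month group, a patient infused early at M2 on the p-CTX trigger who stays on the printed calendar is next sampled at 1, 2, 4 and 7 months after infusion, so 40 may itself be optimistic.

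**Step 4: illustration for one joint model (assumed).** Count gender, age, years of denosumab and one baseline BMD term as 4 predictors. Each marker adds 3: baseline, three-month change and six-month change. Residual df = n − p − 1.
- p-CTX and p-PINP only: p = 4 + 2×3 = 10. At n = 60, df = 49; at n = 40, df = 29.
- All four markers: p = 4 + 4×3 = 16. At n = 60, df = 43; at n = 40, df = 23.

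The smallest partial R² detectable for one predictor (80% power, two-sided 5%, noncentral F on 1 and n − p − 1 df, noncentrality n·R²/(1 − R²)) is about 0.12 at n = 60 for either count. At n = 40 it is 0.174 with 10 predictors and 0.176 with 16.

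**The case against.** The strongest reply is that the text need not mean one joint model. It speaks of analyses in the plural, and its aim refers to changes at three *or* six months. Separate models for baseline factors, three-month changes and six-month changes would fit that wording, and only the three-month ones would lose the observation arm. This stands. A reader might infer that the whole regression exercise excludes that arm; the documents do not support this. The factor list does join the two time points with *and* and refers to a single analysis, so the text is ambiguous, but on either reading the three-month factor cannot be used in the observation group.

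Other stronger readings also go beyond the documents:
- *About 16 predictors, with chance R² rising from 27% (16/59) to 41% (16/39).* The plan never says which markers enter or how many at once. Sixteen is the top of an assumed range; with 10 predictors the figures are 17% (10/59) and 26% (10/39). The plan sets no R² target, and coefficient tests already allow for residual degrees of freedom.
- *The lost arm has the widest range of turnover.* No figure in the documents shows this, and the 9-month group has the same p-CTX trigger.
- *The plan prescribes complete-case analysis.* It does not; it is silent.

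Mx+2 may be a slip for Mx+3, since the other arms use one, three and six months. The documents do not settle this, and if it is a slip, the table still has to be corrected. Finally, this is one exploratory analysis. That is true, and it limits the weight of the point.

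**Conclusion.** The mismatch is certain from the text: the three-month post-infusion marker change is a listed factor, and the infusion-anchored schedule does not supply it in the observation group. Any model containing it has at most 40 of 60 patients, none from that arm. This count rests only on the printed schedule and the planned group sizes. The fall in residual degrees of freedom (49 to 29, or 43 to 23) also assumes a single joint model and 10 or 16 predictors, so it is an illustration.

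Models using baseline factors or the six-month change are unaffected. So are the co-primary and secondary endpoints: none uses a three-month marker value, and the marker endpoints at 6 and 12 months are sampled in every arm. The point is minor and worth correcting because correction is cheap.

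**What to change.** Reconcile the visit table with the factor list in one of two ways.

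1. **Align the schedule.** Place the observation group's second post-infusion marker sample at Mx+3 in place of Mx+2. No sample is added; one is moved. This helps only patients who have not yet passed that visit.
2. **Keep the schedule and change the analysis text.** Base the all-arm regression on marker changes that all three groups have, at one month (M1, M4, Mx+1) and six months (M6, M9, Mx+6). Report any three-month model as limited to the two scheduled-infusion arms. This is wording only; the price is that an earlier change replaces the planned three-month one in the all-arm model.

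In either case, state whether the factors enter one model or several, and include randomised group in the all-arm model. Otherwise a coefficient for marker change mixes differences between arms with the association within arms. Group costs two degrees of freedom: 49 becomes 47 with 10 other predictors, and 43 becomes 41 with 16. The choice of markers is a separate modelling decision that this mismatch does not settle.

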#### **Secondary endpoints**

- Changes in total hip, femoral neck and lumbar spine BMD from baseline to one year after the zoledronic acid infusion.
- Changes in total hip, femoral neck and lumbar spine BMD from baseline to two years after the zoledronic acid infusion.
- Changes in trabecular bone volume fraction (bone volume/tissue volume, BV/TV) and cortical porosity measured by high-resolution peripheral quantitative computed tomography (HR-pQCT) scan at the radius and tibia from baseline to one year after the zoledronic acid infusion.
- Changes in p-CTX and p-procollagen type I N-terminal propeptide (p-PINP) from baseline to six months after the zoledronic acid infusion.
- Changes in p-CTX and p-PINP from baseline to 12 months after the zoledronic acid infusion.
- Morphometric vertebral fractures assessed by vertebral fracture assessment (VFA) one and two years after the zoledronic acid infusion.

---

 Electrochemiluminescence immunoassay (ECLIA) will be used.

 Reference range: Women 30-50 years: 0,04 - 0,59 µg/l. Women > 50 years: 0.03-0.83 µg/l. Men 30-50 years: 0,09 - 0,63 µg/l. Men 50-70 years: 0.04-0.84 µg/l. Men > 70 years: 0,08 – 1,05 µg/l.

 ECLIA will be used.

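### Maintained BMD is accepted when the loss is below 2.5%, but no planned analysis tests a group's mean loss against 2.5%

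*Combined protocol and SAP*

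**What the plan says.** All of the following is in the combined protocol and SAP.

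- **Sample size** (Statistical analysis and power calculation). From a published study, "a 5% decrease in lumbar spine BMD can be expected during the first year after discontinuation with a 3% standard deviation". Eighteen patients per group, raised to 20 for dropouts, are said to be enough to demonstrate a loss of at least 2.5% "using a paired-sample t-test with a power of 90% and level of significance of 5"%. The acceptance rule follows: "If the decrease is less than that BMD is maintained and the hypothesis can be accepted".
- **Analyses of mean change** (same section). "Changes in bone mineral density one year after the zoledronic acid infusion within groups will be investigated using paired-sample t-tests". The changes are also compared with the published change after stopping denosumab, "for the three groups combined and individually using one-sample t-test". A mixed model compares the groups with each other.
- **Patient-level endpoint** (Co-primary endpoint). "The proportion of patients who fails to maintain BMD (total hip, femoral neck and spine") is the second co-primary. A patient fails with a loss of 3% or more at the spine, or 5% or more at either hip site. The groups are compared by chi-square.
- **Time point.** The first co-primary is "Change in lumbar spine BMD from baseline to 6 months after the zoledronic acid infusion". The one-year change is listed as secondary: "Changes in total hip, femoral neck and lumbar spine BMD from baseline to one year after the zoledronic acid infusion". The Duration of study section places the primary endpoints at 12 months after infusion.
- **Intended conclusion.** The Perspectives section says the study will show whether zoledronic acid can preserve bone mass.

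**The concern.** A claim that BMD is maintained asserts that the loss is small. It needs evidence that excludes a loss of 2.5% or more. The plan attaches the claim to a test whose null hypothesis is zero change, so the claim would rest either on failing to find a loss or on a bare point estimate:

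- **Reading A:** the paired t-test against zero is not significant.
- **Reading B:** the observed mean loss is below 2.5%.

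Under A, the chance of wrongly accepting a 2.5% loss depends on n and SD, and noisier data make the claim easier to reach. Under B, that chance is one half whatever the sample size. The readings also disagree. With 20 patients and an observed SD of 3%, a mean loss between 1.4% and 2.5% is a significant loss under A and maintained under B.

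Maintenance of bone mass is the conclusion the Perspectives section promises, so the trial could report opposite headlines from the same data.

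**Working it through.** **Inputs.** From the plan: margin 2.5%, SD of change 3%, significance level 5%, power 90%, 18 patients raised to 20 per group, published loss 5%. Assumed here: a two-sided test (sidedness is not stated), normally distributed changes, other SDs of 2%, 4% and 5%, and true losses of 0 to 3%. The plan gives no expected loss under zoledronic acid.

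**1. Reproduce the plan's n.** For a paired t-test against zero, power is the probability that a noncentral t with n − 1 df and noncentrality 2.5/(3/√n) exceeds t(0.975, n − 1).

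| n | Power |
|---|---|
| 17 | 89.7% |
| 18 | 91.5% |
| 20 | 94.2% |

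Eighteen is the smallest n reaching 90%. The stated figure therefore reproduces, and it is a test against zero.

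**2. Reading A at a true 2.5% loss.** P(accept) = 1 − power: 8.5% at n=18 and 5.8% at n=20. At n=20 with other SDs it is 0.04% (SD 2%), 24.5% (SD 4%) and 43.5% (SD 5%).

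**3. Reading B at a true 2.5% loss.** P(observed mean < 2.5) = Φ(0) = 50% for any n and SD.

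**4. Where the readings part.** At n=20 and observed SD 3%, the smallest significant loss is t(0.975, 19) × 3/√20 = 1.40%. An observed 2.4% loss has a 95% CI of 2.4 ± 1.40, or 1.0% to 3.8%. That excludes zero and runs well past 2.5%, yet it passes under B. The probability of a significant loss together with an observed loss below 2.5%, integrating over the sample SD (n=20, SD 3%), is:

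| True mean loss | Readings disagree |
|---|---|
| 0 | 2.5% |
| 0.5% | 10% |
| 1% | 28% |
| 1.5% | 50% |
| 2% | 58% |
| 2.5% | 44% |
| 3% | 22% |

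**5. Three groups.** If all three truly lose 2.5%, the chance that at least one is called maintained at n=20 is:
- Reading A: 1 − 0.942³ = 16%
- Reading B: 1 − 0.5³ = 87.5%
- 95% confidence-limit rule: 1 − 0.975³ = 7.3%

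**6. Do the other planned analyses fill the gap?**
- *One-sample test against the published loss, taken as a fixed 5%.* At n=20 and SD 3% it is significant for any observed loss below 5 − 1.40 = 3.60%. It supports reduced loss, not a loss below 2.5%.
- *Patient-level failure.* This compares proportions between groups and does not test a group mean. The share of spine failures at mean loss m is 1 − Φ((3 − m)/3), which is 43% at m = 2.5 and 16% at m = 0. Reading B can therefore call a group maintained while about four in ten of its patients count as failing to maintain BMD.
- *Mixed model.* It compares groups with each other, not with a margin.

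**7. The narrower hypothesis.** At a true 5% loss, n=18 and SD 3%, Reading B accepts with probability Φ(−2.5/(3/√18)) = 0.02%, and Reading A less often still. The rule rarely fails there.

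**8. A rule that tests the margin.** Require the upper 95% confidence limit of the mean loss to be below 2.5% (one-sided 0.025). At n=20 and observed SD 3%, the observed loss must be under 2.5 − 1.40 = 1.10%. Power at SD 3%:

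| True mean loss | n=18 | n=20 | n=20, 90% limit |
|---|---|---|---|
| 0 | 91.5% | 94.2% | 97% |
| 0.5% | 76% | 81% | 89% |
| 1% | 52% | 56% | 70% |

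With the 95% limit, 90% power needs 18 per group at zero true loss, 26 at 0.5% and 44 at 1%. At SD 4%, zero true loss and n=20, power is 76%.

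**The case against.** The hypothesis actually stated is that zoledronic acid reduces the expected loss, and that has its own one-sample test. Maintenance has an operational definition in the patient-level co-primary endpoint. The 2.5% figure appears only in the sample-size reasoning. At the planned n=20 and SD 3%, Reading A behaves almost like a 90% confidence limit: it finds no significant loss in 70.7% of trials at a true 1% loss and 5.8% at 2.5%, against 69.5% and 5.0%. The 50% and 87.5% figures come from Reading B alone. Disagreement rates are not error rates, since a loss can be both significant and smaller than a margin; even the confidence-limit rule gives both statements in about 51% of trials at n=20, SD 2% and a true 1.25% loss (about 4% at SD 3%). Finally, 2.5% is nowhere justified as an acceptable loss.

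Much of this stands. The reduced-loss hypothesis is protected, Reading A is tolerable if the planned SD holds, and the disagreement rates measure ambiguity, not error. What does not stand is that the gap is closed. The sentence is an explicit acceptance rule, nothing in the plan selects Reading A, and A's error grows with SD and dropout. The patient-level endpoint gives no criterion for a group mean. When the confidence-limit rule yields a loss that is both significant and within the margin, it has excluded 2.5%; Reading B has not. The missing justification of 2.5% is a reason to state the margin openly.

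**Conclusion.** The concern holds and should be fixed. The plan accepts maintained BMD against a 2.5% threshold that no planned analysis tests. At a true 2.5% loss the claim would be made in 5.8% (n=20) or 8.5% (n=18) of trials on one reading at the planned SD of 3%, and in 50% on the other. The choice of reading matters mainly for true mean losses of about 1% to 3%; with little or no true loss the two mostly agree. The sample size is not wrong, and the reduced-loss hypothesis is adequately tested. These figures assume normal changes; SDs other than 3% and the range of true losses are assumptions, not figures from the plan.

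**What to change.** Replace the acceptance sentence with wording such as:

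> Mean lumbar spine BMD is maintained in a group if the lower limit of the two-sided 95% CI for mean percent change from baseline to one year after the infusion lies above −2.5%. This is a group-mean criterion, separate from the patient-level failure endpoint, and is concluded for each group on its own. Reduced loss is concluded from the one-sample t-test against the published loss, treated as a fixed value.

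Keep the paired t-test against zero as descriptive, and restate power for the new criterion using the table above.

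Two points must be settled at the same time:
- **Time point.** One year fits the planned tests and the first-year benchmark, but the Co-primary endpoint, Secondary endpoints and Duration of study sections must be reconciled. If 6 months is kept, the margin and the published comparison need a 6-month basis.
- **One margin for three groups.** One year after infusion falls 12, 15 and up to 18 months after baseline by group, so the plan should say whether a single margin is meant for all.

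The cost is a few sentences, with no extra patients or data. The price is that maintenance becomes harder to claim when some true loss remains. A 90% limit is a defensible alternative: 5% error at the margin, with the higher power shown.
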